3. STUDY OBJECTIVE AND HYPOTHESIS

SPECIFIC AIM: To establish the feasibility, acceptability, and preliminary efficacy of *PEERNaija*, an mHealth intervention designed to harness peer influence as an incentive to promote medication adherence among a pilot cohort of 50 AYA living with HIV in Nigeria.

[figure not shown]
Hypothesis: *PEERNaija* will be feasible, acceptable, and show preliminary efficacy in improving ART adherence.

4. METHODS (TO INCLUDE STUDY DESIGN, DETERMINATION OF SAMPLE SIZE, EXCLUSION/INCLUSION CRITERIA, ANALYSES OF DATA, ETC.)

Eligibility and Enrollment: We will conduct a prospective pilot study of the *PEERNaija* application for 50 AYA living with HIV in Nigeria. Patients will be recruited from the APIN HIV clinic and will be eligible for this study if they 1) own a smartphone (on which they are willing to download *PEERNaija*), 2) are 14-29 years of age, 3) are on ART, and 4) demonstrate the ability read simple text language in English. Patients will provide written informed consent for study participation.

Intervention Description: All participants will receive daily medication reminders, access to the virtual support group, and other key features identified in Aim 1. In addition, participants will be randomized to receive the social incentive (n=25) or the social plus financial incentive (n=25), *PEER+* and be followed for 24 weeks.

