Study Outcomes: The outcomes of interest for this study are feasibility, acceptability, adoption, and preliminary efficacy, and will be measured at 24 weeks. Preliminary efficacy will be assessed by comparing change in HIV viral load, and adherence from baseline to 12 weeks, and baseline to 24 weeks. We hypothesize that the *PEERNaija* mHealth application will be feasible and acceptable, and show preliminary efficacy in improving HIV virologic control. The study outcomes will be assessed through a combination of a) questionnaires administered to study participants b) clinical measures or correlates of adherence measured at baseline and at each study visit, and (c) analysis of usage data collected during routine use of the application. Chat feature use will be measured by monitoring the monthly frequency of posts per participant in addition to the thematic content.

Data analysis: Study feasibility and acceptability will be measured by analyzing the content of the feedback surveys at each study visit, and the FGDs at study end. Adoption will be assessed by analyzing usage data. Preliminary efficacy will be assessed by conducting a pre–post comparison of adherence measures, HIV viral load, and adoption measures at baseline, 12, and at 24 weeks in the two study groups (*PEER* and *PEER+*). De-identified chatroom the chat posts will be downloaded from the coordinator application, and reviewed from weeks 0-12 and 12-24.

5. ETHICAL CONSIDERATION. CONSENT DOCUMENTATION (TRANSLATION TO LOCAL LANGUAGES WHERE APPLICABLE) AND PATIENT INFORMATION LEAFLET (WHERE APPLICABLE)

A. Risks to the Subjects

A.1. Human Subjects Involvement and Characteristics. This study will involve several participants, namely:

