Comparisons of primary outcomes (feasibility, acceptability and appropriateness) will be performed by comparing mean FIM, AIM, and IAM scores respectively between PEERNaija and PEERNaija+ at 24 weeks using two-sample t-tests. These constructs will additionally be addressed by comparing questions from feedback questionnaires, specifically assessing percentage of reminders received and whether or not reminders or chat messaged were intrusive, whether it was helpful to see their peers' adherence scores, whether they would use the app after the study, and whether they would recommend the app to a peer.

Comparisons between secondary outcomes (viral load and self-reported adherence) will be assessed by conducting a pre-post comparison of adherence measures at baseline, 12, and at 24 weeks, and pre-post comparison of viral load measures at baseline and 24 weeks in the two study groups (*PEERNaija* and *PEERNaija+*), using paired tests (e.g., paired t-tests, signed rank tests, or McNemar's tests, as appropriate), with a significance level set at $p \leq .05$ (2-tailed test). Further, self-reported preliminary efficacy will be assessed via response to feedback questionnaire question asking whether the app helped them to miss fewer medication doses and responses across study groups using Chi-square tests.

To further explore associations between outcomes and variables of interest, univariate regression analyses will be performed. Linear regression will be applied to continuous outcomes, including the primary outcomes (FIM, AIM, and IAM score) and self-reported adherence; while logistic regression will be used for binary outcomes such as viral suppression status at the study end.

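### The efficacy aim concerns one cohort of 50 who all receive the app, but the paired pre-post tests are specified by arm of 25 and no pooled estimate is planned

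*Combined protocol and SAP*

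**What the plan says.** Section 3 (Specific Aim) sets out to establish feasibility, acceptability and preliminary efficacy of the app "among a pilot cohort of 50 AYA living with HIV in Nigeria". Section 4 (Intervention Description) says: "All participants will receive daily medication reminders, access to the virtual support group, and other key features identified in Aim 1". Participants are then randomised 25 and 25 to the social incentive alone or the social plus financial incentive. Both arms therefore have the app and the social incentive. PEER+ adds the monthly lottery and its weekly loss-framed messages.

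The SAP (section 6, Analysis Plan) assesses the secondary outcomes by a pre-post comparison of adherence at baseline, 12 and 24 weeks and a "pre-post comparison of viral load measures at baseline and 24 weeks in the two study groups". The tests are "paired t-tests, signed rank tests, or McNemar's tests, as appropriate", two-sided at the .05 level. Section 4 (Data analysis) has the same structure: a pre-post "comparison of adherence measures, HIV viral load, and adoption measures at baseline, 12, and at 24 weeks in the two study groups".

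Neither section names a paired analysis of all participants together. No power, effect size, SD or dropout figure is given for any analysis.

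**The concern.** Paired tests measure within-person change; they do not compare the arms. If each is run within an arm, the cohort-level question in the aim is addressed twice with half the data, and no specified analysis addresses it with all the data. Each arm's interval is wider than the study can deliver. The reader is also left to combine two p-values without a rule: counting significance in either arm inflates the false-positive risk, and requiring it in both is very demanding. Section 7 says the pilot will be the basis for a larger trial, so the precision of the one estimate that matches the aim is worth having.

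**Working it through.** There is no stated power figure to reproduce. The check compares n=25 (one arm) with n=50 (both arms pooled), assuming equal change in the two arms and, except where stated, no dropout.

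**Inputs from the documents.** N=50 and 25 per arm (section 4); two-sided .05 and the list of paired tests (section 6). The 40% virologic failure figure in section 2 comes from a retrospective analysis of young patients still in care a year after starting ART. It is used here only as an assumed baseline proportion unsuppressed.

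**Assumed.** Standardised paired effect d from 0.2 to 0.6. For suppression: half of the unsuppressed convert and 5% of the suppressed rebound, with ranges below.

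**1. Interval width.** The half-width of a 95% CI for mean change is t(0.975, n−1) × SD/√n.
- n=25: 2.064/5 = 0.413 SD
- n=50: 2.010/7.071 = 0.284 SD

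The sample-size factor alone is √(50/25) = 1.41; with the t multipliers the ratio is 0.413/0.284 = 1.45. So about 1.4.

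**2. Paired t-test.** Power comes from the noncentral t distribution with n−1 degrees of freedom and noncentrality d√n. The effect detectable with 80% power is 0.58 SD at n=25 and 0.40 SD at n=50.

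| d | n=25 | n=50 | relative loss |
|---|---|---|---|
| 0.2 | 16% | 28% | 43% |
| 0.3 | 30% | 55% | 45% |
| 0.4 | 48% | 79% | 39% |
| 0.5 | 67% | 93% | 28% |
| 0.6 | 82% | 99% | 17% |

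The largest relative loss at any d is 45%.

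**3. McNemar test on suppression.** With proportion u unsuppressed and c converting, gain = u×c and loss = 0.05×(1−u). In the central case gain = 0.40×0.50 = 0.20 and loss = 0.05×0.60 = 0.03. Power was obtained by enumerating the discordant pairs.

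| Version | n=25 | n=50 | relative loss |
|---|---|---|---|
| Exact | 23% | 66% | 65% |
| Mid-p | 37% | 75% | 51% |
| Uncorrected chi-square | 45% | 75% | 40% |

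The exact test is costly in a small arm because six conversions with no rebound are needed (2×0.5⁶ = 0.031, against 2×0.5⁵ = 0.0625 for five).

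**4. Range for the exact test.** Over u = 30–50% and c = 40–60%, power is 4–61% at n=25 and 20–96% at n=50, a relative loss of 36–82%. At u = 60% and 70% with half converting, the loss falls to 33% and 18%.

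**5. Dropout.** With 20 and 40 completers, central-case exact McNemar power is 13% against 52%. Paired t-test power at d=0.4 is 40% against 69%, a 43% loss.

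**6. Reading two arm-level tests together.** With equal effects, the chance that neither arm reaches significance is (1−power)²:
- exact McNemar, central case: (1−0.232)² = 59%
- uncorrected McNemar, central case: (1−0.449)² = 30%
- paired t-test at d=0.4: (1−0.484)² = 27%

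If significance in either arm counted, the false-positive risk under no change would be 1−0.95² = 9.8%. If both arms were required, paired t-test power at d=0.4 would be 0.484² = 23%.

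**The case against.** **The text does not rule out pooling.** This stands. The SAP does not use the word separately, the secondary outcome is defined without restriction to an arm, and the descriptive statistics at baseline and follow-up could cover the whole cohort. A reader might infer that the cohort will never be analysed as a whole; the documents show only that a pooled paired estimate is not specified. The other analyses do not replace it. The descriptive plan gives means and standard errors of variables, and without the within-person correlation these do not yield an interval for change. The regressions are not paired analyses.

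**The size of the loss is easily overstated.** This also stands. A reader might infer that splitting by arm removes about two thirds of the power. That is one scenario under the exact McNemar test, which the SAP does not name; the paired t-test, listed first, never loses more than 45%. A reader might likewise infer that two non-significant results are likely. That holds in the central exact case (59%) but not for uncorrected McNemar (30%) or a paired t-test at d=0.4 (27%). The 40% baseline figure is also borrowed: section 5 (A.1) requires documented poor adherence, which section 4 does not list, and a higher unsuppressed proportion would shrink the loss.

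**Arm-level change is legitimate.** Agreed. The arms receive different incentive packages, so calling the split needless goes too far. The arm-specific results should stay; they are simply not the estimate that the aim describes.

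**This is an uncontrolled pilot comparison on a secondary outcome.** True, and pooling does not turn change into an app effect. Regression to the mean could produce improvement, especially if the poor-adherence criterion applies. But this affects the arm-level tests equally, so it is a reason for careful labelling and not for the wider interval.

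**Conclusion.** The point holds as a mismatch between aim and analysis: the aim concerns 50 participants who all use the app, the paired tests are described by group of 25, and no pooled paired estimate is specified. Specifying one is a cheap improvement to a secondary analysis; its absence does not threaten the primary outcomes.

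The firmest figures are the narrowing of the interval by about 1.4 and the fall in detectable effect from about 0.58 to 0.40 SD. Both assume similar change and similar variability in the two arms, and full follow-up. The relative power loss per arm has no single value. It is about 17–45% for a paired t-test at d 0.2–0.6. With 40% unsuppressed, half converting and 5% rebounding, it is about 40% for uncorrected and 65% for exact McNemar, and 36–82% for the exact test over the stated ranges. The documents do not support a general two-thirds loss, a claim that the split serves no purpose, or a claim that whole-cohort analysis is excluded.

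**What to change.** Add to the SAP Analysis Plan a single pooled paired estimate with 95% CI, in all participants with paired data, for change from baseline to 24 weeks in viral load and in adherence. Name it as the estimate that answers the cohort-level aim. Label it as uncontrolled change that regression to the mean could produce. Keep the arm-specific changes alongside, each with its own interval, and make the matching edit to Data analysis in section 4.

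The cost is a sentence or two of SAP text and one more table row, from data already being collected. The small downside is that the pooled figure averages two incentive packages; the table should say so.

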6. STATISTICAL ANALYSIS PLAN (SAP)

Primary Outcomes

Primary outcomes are feasibility, acceptability, and appropriateness of the PEERNaija app. These will be assessed through Weiner’s validated feasibility of intervention measure (FIM), acceptability of intervention measure (AIM), and appropriateness of intervention measure (IAM) at six months. The FIM, AIM, and IAM surveys each contain four statements and participants are asked to rate their level of agreement to each statement on a Likert scale of 1-5, with 1 being “completely disagree” and 5 being “completely agree.”

Participants will answer study team-generated questions assessing the acceptability and appropriateness of individual app features and the app overall via feedback questionnaires administered at 12 and 24 weeks.

Secondary Outcomes

Secondary outcome is preliminary efficacy on viral load. This will be assessed by comparing change in HIV viral load (from baseline to 24 weeks), and self-reported adherence from baseline to 12 weeks, and baseline to 24 weeks. ART adherence will also be assessed at baseline and six months using a visual analogue scale where participants indicated the percentage of prescribed ART doses taken over the past 30 days.

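### The trial randomises 25:25 to PEER or PEER+, but the SAP gives viral load and self-reported adherence only within-arm paired tests and no between-arm test or estimate

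*Combined protocol and SAP*

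**What the plan says.** Section 4 (Intervention Description) sets up a randomised comparison: "participants will be randomized to receive the social incentive (n=25) or the social plus financial incentive (n=25"), with 24 weeks of follow-up. All participants receive the app.

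The Secondary Outcomes part of SAP section 6 describes preliminary efficacy as follows: "This will be assessed by comparing change in HIV viral load (from baseline to 24 weeks), and self-reported adherence from baseline to 12 weeks" and to 24 weeks. It does not say whether change is compared within or between arms.

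The Analysis Plan part of section 6 then names the method. Adherence is compared at baseline, 12 and 24 weeks. Viral load gets a "pre-post comparison of viral load measures at baseline and 24 weeks in the two study groups", "using paired tests (e.g., paired t-tests, signed rank tests, or McNemar's tests, as appropriate), with a significance level set at" 0.05, two-tailed. Data analysis in section 4 gives the same approach: "Preliminary efficacy will be assessed by conducting a pre–post comparison of adherence measures, HIV viral load, and adoption measures".

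The same SAP section does name between-arm tests for other outcomes: two-sample t-tests for the FIM, AIM and IAM scores, and a Chi-square test across groups for one feedback item on whether the app helped participants miss fewer doses.

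The last analysis paragraph adds: "To further explore associations between outcomes and variables of interest, univariate regression analyses will be performed". The outcomes include self-reported adherence (linear) and suppression at study end (logistic). Study arm is not named as a predictor.

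**The concern.** The three tests offered for the efficacy outcomes (paired t, signed rank, McNemar) all compare a participant's later value with that participant's own baseline. None compares PEER with PEER+. The plan therefore tests the arms against each other on opinions of the app, but not on viral load or measured adherence, which the added financial incentive is meant to change.

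Within-arm change does bear on the hypothesis about the app as a whole, but it cannot separate an app effect from time, study attention or regression to the mean. Regression to the mean is a concrete risk here. Section 5 (A.1) lists documented poor adherence as an eligibility criterion for the pilot, although section 4 omits it. If it is applied, people selected for poor values will tend to improve with no app effect at all. Randomisation protects the between-arm difference from these influences, and that difference is what the plan does not produce.

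The SAP does not say that the two arms' p-values will be compared. With no direct contrast planned, though, a result significant in one arm only could easily be read as an effect of the financial incentive. Section 7 says the project is to be the basis for a larger trial, so such a misreading could carry forward.

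**Working it through.** The documents give no power, target effect, SD or dropout figure for the trial, so there is no stated calculation to reproduce.

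**Inputs from the documents.** 25 per arm (section 4); two-sided 0.05 (section 6). Background only: 40% virologic failure in an earlier Nigerian cohort, so about 60% suppressed (section 2).

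**Assumptions.** Standardised true changes of 0 to 0.8 SD, where the SD is that of the individual changes; baseline/24-week correlations r of 0.3, 0.5 and 0.7; suppression of 60% vs 80%; adherence-change SDs of 15 to 30 points; no dropout unless stated.

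**Step 1: what two separate paired tests can show.** Let p be the power of a paired t-test with n = 25 (noncentral t, 24 df, noncentrality d√25). If both arms have the same true change d and are independent, the chance that exactly one arm is significant is 2p(1−p).

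| True change in both arms (SD) | p | 2p(1−p) |
|---|---|---|
| 0 | 0.050 | 9.5% |
| 0.1 | 0.077 | 14% |
| 0.2 | 0.161 | 27% |
| 0.3 | 0.302 | 42% |
| 0.4 | 0.484 | 50% |
| 0.5 | 0.670 | 44% |
| 0.6 | 0.821 | 29% |
| 0.7 | 0.919 | 15% |
| 0.8 | 0.970 | 6% |

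Example at 0.3 SD: 2 × 0.302 × 0.698 = 0.422. In every row the arms do not differ, and a direct between-arm test would be falsely positive 5% of the time.

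**Step 2: what a direct contrast would deliver, continuous outcomes.** From here the SD is that of the outcome at a single time point.

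- Follow-up-only two-sample t-test, 80% power: detectable difference 0.809 SD.
- Change score: 0.809 × √(2(1−r)) = 0.96, 0.81 and 0.63 SD at r = 0.3, 0.5 and 0.7.
- ANCOVA: 0.809 × √(1−r²) = 0.77, 0.70 and 0.58 SD.
- Unadjusted 95% CI half-width: t(48) × √(2/25) = 2.011 × 0.283 = 0.57 SD.
- ANCOVA half-width: t(47) × √(2/25) × √(1−r²) = 0.49 SD at r = 0.5 and 0.41 SD at r = 0.7.
- In adherence points, for an SD of change of 15, 20, 25 or 30 points: 0.569 × SD = 8.5, 11.4, 14.2 or 17.1 points either side.
- With 22 or 20 analysed per arm, the unadjusted detectable difference rises to 0.86 or 0.91 SD and the half-width to 0.61 or 0.64 SD.

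**Step 3: suppression.** Take 15/25 (60%) vs 20/25 (80%). The Wilson limits are 0.407 to 0.766 and 0.609 to 0.911. Newcombe limits for the difference of 0.20:

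- Lower: 0.20 − √((0.80−0.609)² + (0.766−0.60)²) = −0.05.
- Upper: 0.20 + √((0.911−0.80)² + (0.60−0.407)²) = +0.42.

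Power for this difference is about 33%.

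**Step 4: could the regressions fill the gap?** Arm is not named among the variables of interest. If arm were the single predictor, the model would give a valid randomised estimate, but a one-predictor model has no room for the baseline value. The logistic outcome is status at study end. The plan permits such an analysis but does not specify it.

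**The case against.** The strongest reply is that the stated hypothesis concerns the app as a whole: it "will be feasible, acceptable, and show preliminary efficacy in improving ART adherence". No section claims that PEER+ beats PEER, efficacy is secondary, and this is a pilot of 50. Pre-post testing answers the question as posed. That stands in part: it is a reason to keep the within-arm estimates and to avoid a confirmatory claim. It does not explain why a trial that randomises leaves its only randomised efficacy contrast unplanned.

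A second reply is that arm could enter the univariate regressions, and that the loose wording about comparisons in the two study groups may have been meant as an arm comparison. Both are possible. If so, the text needs correcting, because the tests it names cannot do this.

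Third, the one-arm-only percentages describe a misreading that the SAP does not plan. That is right: they show why a direct contrast is needed and do not measure an error in a planned test.

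Three practical points also stand. Dropout would widen the intervals. If the support group or peer displays span the arms, which the documents do not settle, contamination could dilute the contrast. Viral loads below the assay limit, likely to be common on ART, need a rule before any model on the log scale.

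**Conclusion.** The concern holds. For viral load and self-reported adherence the SAP specifies no between-arm test, estimate or confidence interval. The between-arm tests it does name cover the FIM, AIM and IAM scores and one perceived-benefit item.

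The consequence is moderate. These are secondary outcomes in a pilot, and even the right contrast is imprecise: it could detect roughly 0.6 to 0.8 SD with ANCOVA at 80% power, and a 20-point difference in suppression would be compatible with anything from about −5 to +42 points. These figures rest on 25 analysed per arm and on the assumed correlations and rates. The 60% suppression figure matches the background cohort in section 2, but the documents give no design assumption for any of these quantities. The textual finding depends on none of them. It should be fixed before analysis.

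**What to change.** Amend the Analysis Plan in SAP section 6 to prespecify, for each efficacy outcome, a PEER+ minus PEER estimate with a 95% CI, adjusted for the baseline value:

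- **Viral load:** ANCOVA of log10 viral load at 24 weeks on arm and baseline, with a stated rule for values below the assay limit. Section 6 schedules viral load at baseline and 24 weeks only, while section 4 also mentions 12 weeks, so reconcile the two.
- **Self-reported adherence:** ANCOVA at 24 weeks, or a mixed model over 12 and 24 weeks for measures collected at both visits. Section 6 gives the visual analogue scale at baseline and six months only.
- **Suppression at 24 weeks:** logistic regression with arm and baseline suppression, or a risk difference with its CI.

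Keep the within-arm pre-post changes as descriptive estimates with CIs, and state that they do not compare the arms. State also that the between-arm contrast is imprecise at this sample size and serves planning, not confirmation.

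The cost is SAP wording and a little extra analysis, with no new patients, visits or measurements. The downside is a wide interval that must be reported as such.

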For the **social incentive**, the application will track the participant's individual adherence score (% of doses taken), track the top scorers (leaderboard), and provide a figure highlighting the proportion of their peers with poor (<80%), medium (80-94%), or high (>94%) adherence scores. The display of the individual's adherence score relative to peer scores is considered a descriptive norm and is meant to portray "what most people are doing," as young people often inaccurately estimate behaviors for their peer groups. Participants will also receive an injunctive norm, or an indication of what they ought to be doing. This will come in the form of an emoji or congratulatory vs. motivating text for those with high or low adherence scores, respectively. When coupled with descriptive norms, injunctive norms have counteracted regression to the mean for individuals who demonstrate desirable behaviors relative to their peers.²⁸ For the **financial incentive**, the top 5 scorers in the *PEER+* arm will be eligible win a lottery prize each month of the 24 week pilot of 1000 NGN of "data" that can be directly loaded onto the winner's phone [Figure 1]. Behavioral economics theory tells us that individuals are more averse to losses than rewarded by gains, so that even incentives/prizes should be framed in terms of losses.⁴⁰ Accordingly, participants in the financial incentive arm will receive weekly motivating messages such as "take your dose today or you lose the chance of winning the lottery." Potential language for these messages will be informed by user-centered feedback in Aim 1.

Patients will be seen in clinic at enrollment, 6 weeks, 12 weeks, and 24 weeks. At enrollment, patients will complete a comprehensive survey assessing demographics and mobile phone usage patterns. We will also collect data on a range of factors known to impact medication adherence including, depression (WHO SQ-20 scale), self-efficacy (medication taking self-efficacy scale), stigma (Berger's HIV stigma scale), symptoms (HIV symptom severity scale), and social support (SPS-10 scale).⁵⁵⁻⁵⁸ Adherence will be assessed using from the application itself (percentage of doses completed) and from 3 validated measures: 1) self-reported visual analog scale (VAS), 2) medication possession ration (MPR), and 3) AIDS Clinical Trials Group (ACTG)

adherence questionnaire.⁵⁹⁻⁶¹ Baseline CD4 count and HIV RNA will be obtained from the clinic record (within 3 months of enrollment).

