Additional covariates are assessed at baseline, and include depression, digital health care literacy, self-reported ART self-efficacy and adherence, HIV stigma, social support, and alcohol and substance use. Depression was assessed through the Patient Health Questionnaire, version 9 (PHQ-9). The PHQ-9 contains 9 items on the frequency of depressive symptoms in the past two weeks; total scores range from 0-27 and higher scores indicate a higher severity of depressive symptoms. Digital health care literacy will be assessed through the Digital Health Care literacy scale. The Digital Health Care Literacy Scale contains 3 items on comfort and ability with using technology; total scores range from 0-12 and higher scores indicate higher literacy. ART self-efficacy will be assessed through the HIV Medication Taking Self-efficacy Scale (MT SES). The MT SES contains 16 items on confidence in managing HIV treatment; total scores range from 1-10 and higher scores indicate higher self-efficacy. HIV stigma was assessed through Berger's HIV Stigma Scale. Berger's stigma scale contains 40 items on perceived stigma, fears related to disclosure, negative self-image due to HIV status, and perceived community stigma; total scores range from 40-160 and higher scores indicate higher HIV stigma. Social support will be assessed through the Social Provisions Scale. The Social Provisions Scale contains 24 items on support individuals receive from their social networks; total scores range from 24-96 and higher scores indicate higher social provisions. Alcohol and substance use was assessed through the CRAFFT screening tool. CRAFFT contains 3 items on substance use in the past twelve months; total scores range from 0-3 and higher scores indicate a need for further assessment.

Analysis Plan

Descriptive analyses will be performed to describe the distributional statistics of interested variables, including demographic variables, clinical, and psychosocial characteristics, at baseline and during follow-up assessments. For continuous variables, the mean and standard error will be reported; for categorical variables, frequencies and percentages will be presented.

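### The exploratory linear models for self-reported adherence have one predictor each and so leave out the baseline VAS value that the trial collects (minor)

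*Combined protocol and SAP*

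**What the plan says.** The last paragraph of the SAP's Analysis Plan (section 6) reads "To further explore associations between outcomes and variables of interest, univariate regression analyses will be performed". It continues: "Linear regression will be applied to continuous outcomes, including the primary outcomes (FIM, AIM, and IAM score) and self-reported adherence". For binary outcomes, "logistic regression will be used for binary outcomes such as viral suppression status at the study end". The paragraph does not list the variables of interest. It does not give the time point of the adherence outcome, or say whether that outcome is a level or a change. No multivariable or baseline-adjusted model appears elsewhere in the document.

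The data for adjustment are planned. On adherence: "ART adherence will also be assessed at baseline and six months using a visual analogue scale". On viral load, section 4 (Methods) has: "Baseline CD4 count and HIV RNA will be obtained from the clinic record (within 3 months of enrollment". The candidate covariates are described in section 6: "Additional covariates are assessed at baseline, and include depression, digital health care literacy, self-reported ART self-efficacy and adherence", followed by stigma, social support and substance use. Baseline adherence is therefore itself a listed covariate.

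The design is randomised: "participants will be randomized to receive the social incentive (n=25) or the social plus financial incentive (n=25". For viral load and self-reported adherence, the SAP names paired tests within the two groups. The only test across groups that it names under efficacy is a chi-square test on a feedback question about missed doses.

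**The concern.** Section 4 introduces depression, self-efficacy, stigma and social support as already-recognised influences on adherence. On that premise, these scales will correlate with adherence at baseline. Baseline adherence will in turn correlate with adherence at 24 weeks. A one-predictor model cannot separate a covariate that says something about the following 24 weeks from one that only marks who was adherent at enrolment.

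Two things are at stake. First, section 7 presents the pilot as the groundwork for a larger trial. A covariate list read as predictors beyond baseline could steer stratification or targeting there. Second, the regressions are the only method the SAP lists that could give a between-arm estimate for adherence. If arm is entered alone, that estimate is less precise than data already in hand would allow.

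**Working it through.** The plan gives no figure to reproduce: the sample size of 50 comes without a power or precision calculation.

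**Inputs.** From the documents: N = 50, 25 per arm. Two-sided 0.05 is stated for the paired tests and assumed here to carry over. Assumed, because the documents give no values: the correlation r between a covariate and baseline adherence, the correlation ρ between baseline and 24-week adherence, approximately normal scores, and no effect of the covariate on week 24 once baseline is known.

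**1. Covariate coefficient.** Under these assumptions the covariate's marginal correlation with the 24-week value is r × ρ. Simulating at N = 50:

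| r | ρ | r × ρ | p<0.05, covariate only | p<0.05, baseline added |
|---|---|---|---|---|
| 0.3 | 0.4 | 0.12 | 14% | 5% |
| 0.4 | 0.5 | 0.20 | 29% | 5% |
| 0.5 | 0.6 | 0.30 | 57% | 5% |

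With r = 0 the covariate-only rate stays near 5%.

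**2. What those rates are.** Simulating two variables with true correlation 0.12, 0.20 or 0.30 and no baseline structure gives 14%, 29% and 57%. The covariate-only rates are therefore the power to detect a real marginal association. They are not the error rate of an invalid test.

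**3. Role of arm.** With r = 0.5, ρ = 0.5 and an arm effect of 0.5 SD, the covariate is flagged in 40.7% of trials with the covariate alone, 41.7% with arm added, 5.4% with baseline added and 5.0% with both. Baseline makes the difference and arm does not.

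**4. Precision of an arm comparison.** In a linear model, adding baseline multiplies the standard error of the arm effect by about √(1 − ρ²).

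- ρ = 0.5: √0.75 = 0.87, a 13% cut
- ρ = 0.6: √0.64 = 0.80, a 20% cut
- ρ = 0.7: √0.51 = 0.71, a 29% cut

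Simulation at N = 50, which allows for the lost degree of freedom and chance imbalance, gives about 12-28% over ρ = 0.5-0.7. In SD units the unadjusted standard error is √(2/25) = 0.283. It falls to 0.283 × 0.88 = 0.249 at a 12% cut and to 0.283 × 0.72 = 0.204 at a 28% cut.

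**5. Precision of a covariate coefficient.** The adjusted-to-unadjusted ratio is √[(1 − ρ²) / ((1 − r²ρ²)(1 − r²))].

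- r = 0.4, ρ = 0.5: √[0.75 / (0.96 × 0.84)] = 0.96
- r = 0.3, ρ = 0.6: √[0.64 / (0.9676 × 0.91)] = 0.85
- r = 0.5, ρ = 0.4: √[0.84 / (0.96 × 0.75)] = 1.08

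The gain in step 4 therefore belongs to the arm effect. For covariates, precision can move either way.

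**6. Logistic model for suppression.** The background sections give virologic failure of 30-50% in this age group (section 1) and 40% in a local cohort (section 2); the enrolled group may differ. Of 50 participants, 50 × 0.30 = 15 to 50 × 0.50 = 25 fall in the smaller outcome class. With covariate, baseline and arm that leaves 15/3 = 5 to 25/3 ≈ 8 per parameter, against 15-25 with one predictor. The mechanism in step 1 still applies: over r = 0.3-0.5 and ρ = 0.5-0.7, a covariate with no effect given baseline is flagged in 11-46% of trials unadjusted and about 4% adjusted. Here, though, adjustment has a real cost.

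**The case against.** The strongest reply is that the SAP promises only to explore associations, and a marginal association is a legitimate thing to estimate. Conditioning on baseline adherence, measured at the same visit as the scales, changes the question rather than correcting an error. Steps 1 and 2 bear this out, and the objection stands to that extent. What remains is that the SAP does not label these results descriptive and plans no model that answers the other question.

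A reader might infer several stronger things that the documents do not support:

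- *The plan will mistake pre-existing differences for predictors.* This depends on r and ρ, which the documents do not give, and disappears at r = 0. It also needs someone to read a marginal association as one beyond baseline.
- *Omitting arm produces false predictors.* Arm is randomised and so independent of baseline covariates in expectation; step 3 shows no inflation. Nor does the SAP exclude arm or baseline adherence as a single predictor.
- *These models were meant to show for whom the app works.* The SAP does not say so. Both arms receive the app, and a main-effects model could not show differential response with or without baseline.
- *The plan regresses end-of-study adherence.* Study end is attached only to suppression; for adherence the time point is open.

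It is also fair to say that one-predictor logistic models are defensible at this sample size. The FIM, AIM and IAM scores are planned only at six months, so the baseline point cannot apply to them.

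**Conclusion.** The point holds for the linear adherence models. As written, they cannot distinguish a covariate that adds information beyond baseline from one that tracks baseline. An arm comparison run through them would also forgo a standard-error reduction of about 12-28%, assuming a baseline-to-24-week correlation of 0.5-0.7 and a roughly linear relation on the VAS scale. A lower correlation would give a smaller gain. For viral suppression, adjustment is a trade-off and not a clear improvement. Severity is minor: the step is exploratory and leaves the primary t-tests and the secondary paired comparisons untouched.

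**What to change.** In the regression paragraph of section 6, list the variables of interest and replace the one-predictor rule for adherence with wording such as:

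> *The adherence outcome is the VAS percentage at 24 weeks. Each linear model for adherence will include the covariate, baseline VAS and randomised arm; where the covariate is arm or baseline VAS itself, the model will contain those two terms. Estimates and 95% confidence intervals will be reported as exploratory. Unadjusted associations will also be shown and labelled descriptive.*

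For suppression, keep the one-predictor logistic model as descriptive. A model adjusted for baseline log10 HIV RNA with Firth penalisation can be named as an optional sensitivity analysis, given about 15-25 participants in the smaller outcome class.

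The cost is SAP wording, one or two degrees of freedom (residual 48 to 47 for an arm model, 48 to 46 for a covariate model, with 50 complete cases) and a little more analysis. No new data are needed.
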